### 6.5.2 Infusion Interruption/Dose Modification due to Neurologic Events

In case of grade 3 or higher (for adult subjects) or grade 2 or higher (for pediatric subjects) neurologic adverse events related to blinatumomab, blinatumomab will be stopped immediately and a physical exam, vital signs and safety laboratory tests will be performed. Additional measures can be taken upon discretion of the investigator, depending on the nature of the adverse event. Diagnostic measures to exclude potential infectious causes should be conducted. Assessments of CSF should be performed for cytology, cell count, B- and T-cell measurement flow (flow cytometry at local lab), and viral studies (herpes simplex virus types 1 and 2 (HSV ½), human herpes virus (HHV-6, JC virus and adenovirus). Additional investigations of the CSF should be performed as clinically appropriate.

If the neurologic event has resolved to ≤ grade 1 within 1 week, treatment may be restarted within 2 weeks, but not earlier than 3 days after infusion was stopped.

After treatment interruption, a new treatment cycle may be started after consultation with an Amgen medical monitor. Following dexamethasone premedication as described in Table 4, a new treatment cycle will start at the lower dose level for a subject's assigned cohort. There will be no dose escalations after blinatumomab treatment has restarted following an event.

Date: 20 March 2019 Page 55 of 122

If the event was a  $\geq$  grade 2 seizure, appropriate prophylactic anticonvulsant treatment (eg, a therapeutic dose of phenytoin or levetiracetam) will be administered during the next treatment cycle.

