### 2.3 **Pediatric Risk Assessment**

As of 10 October 2014, 615 adult subjects and 93 pediatric/adolescent subjects have been treated with blinatumomab CIVI. The vast majority of adverse events observed during blinatumomab treatment were transient and completely reversible. The most common events were fever, chills, and headache. Most were observed only during the first days of treatment.

The most medically significant adverse events observed during blinatumomab treatment were neurologic events of grade 2 or 3 and CRS of grade 3 or 4.

Laboratory adverse events observed during treatment with blinatumomab were transient elevations of transaminases.

The present risk profile is balanced by benefits of a high rate of durable responses in the recently conducted Phase 1/2 clinical trial MT103-205 in the same pediatric population, where 37% of all subjects achieved complete hematological remission (von Stackelberg, 2013).

In a relapsed pediatric ALL patient population, the risk of tumor lysis and CRS is considered to be high. Subjects with a high leukemia burden at screening will receive a pre-phase of dexamethasone to reduce the risk of adverse events of cytokine release and tumor lysis and their sequelae. If clinically relevant tumor lysis or CRS are observed, treatment will be interrupted until resolution and the dosing schedule will be modified by an algorithm with step-wise dose increase until maintenance dose.

In the case of a neurologic adverse event, dexamethasone should be administered at a total daily dose of at least 0.2 to 0.4 mg/kg/day (maximum 24 mg per day), divided into 3 doses per day (preferably intravenous [IV]) for up to 3 days. The dose will then be reduced step-wise by at least 25% per day over a maximum of 4 days or as otherwise appropriate per investigator. Restart of blinatumomab treatment will be performed by an algorithm with step-wise dose increase until maintenance dose.

An increased risk of infection may exist, since any long-term IV treatment is associated with the risk of catheter infections and sepsis. Also, blinatumomab-mediated depletion of B cells could result in an increased infection rate. Subjects should be monitored intensely during the first 9 days of the first induction cycle and the first 2 days of subsequent cycles, as well as after any dose step to allow for management of infections and any other adverse events.

Product: Blinatumomab
Protocol Number: 20130265

Date: 20 March 2019 Page 30 of 122

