### 6.5.1.2 **Pediatric Subjects**

Blinatumomab treatment will be interrupted until the following events resolve to ≤ grade 1:

- Grade 2 or higher CRS, tumor lysis syndrome, and DIC/coagulopathy related to blinatumomab
- Grade 2 clinically relevant neurologic event related to blinatumomab, as defined in Appendix I
- Any grade 3 or higher clinically relevant adverse event related to blinatumomab

CTCAE grade 4 adverse events not defined solely based on laboratory parameters at least possibly related to blinatumomab will require permanent discontinuation of blinatumomab. Independent investigator assessment should be used to determine the

Page 52 of 122

Product: Blinatumomab

Date: 20 March 2019 Page 53 of 122

risk:benefit for each individual subject to continue blinatumomab therapy with or without dose reduction or discontinue therapy for:

Grade 4 adverse events that are numerically defined laboratory parameters

 All other grade 3 adverse events and clinically significant laboratory value changes

If the adverse event resolves to  $\leq$  grade 1, blinatumomab may be restarted at the lowest starting dose of the dose cohort for at least 7 days before increasing to a maximum of 15  $\mu$ g/m²/day.

Laboratory assessments will be performed during cycle 1 on days 1 and 2 for the monitoring of tumor lysis syndrome. If a CRS, tumor lysis syndrome, or DIC are observed during week 1, dose modifications will be made as outlined in Table 5. If this dose reduction occurs during cycle 1, the DLT observation period will be extended for an additional 7 days.

Table 5. Treatment Modification for Reversible CRS, Tumor Lysis Syndrome, and DIC

Current Dose	Week 1	Week 2 (Day 8)	Week 3-4 (Day 15)
5 μg/m²/day	3.75 μg/m²/day	5 μg/m²/day	15 μg/m²/day
15 μg/m²/day	5 μg/m²/day	15 μg/m²/day	15 μg/m²/day
10 μg/m²/day	5 μg/m²/day	10 μg/m²/day	10 μg/m²/day

Restart of the infusion should be performed under supervision of the investigator. Before blinatumomab is restarted, premedication with dexamethasone must be administered as described in Table 4. The subject should be observed overnight for possible side effects after the restart.

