In addition to the events described above, the dose may be temporarily or permanently reduced to the lower assigned dose level, if, by investigator's judgment, it is necessary for safety reasons. After at least 7 days of dosing at the lower assigned dose level, the dose may be increased to the highest assigned dose level or treatment may be continued at the lowest assigned dose level after consultation with an Amgen medical monitor. This does not apply for neurologic events as outlined in Appendix I

If the interruption after an adverse event is less than 7 days, the same cycle will be continued. The infusion duration before and after an interruption should total 28 days per treatment cycle. If an interruption due to an adverse event is greater than 7 days, a new cycle will start. In addition, an incomplete treatment cycle with a treatment duration

Product: Blinatumomab

Date: 20 March 2019 Page 54 of 122

of less than 2 weeks will not be counted as an evaluable cycle for the primary endpoint and will have to be repeated (eg, if cycle 1 was interrupted on day 8 for more than 7 days, the next cycle will be denoted as cycle 1.1 and the same assessments will be performed as in cycle 1). For cycle 1.1, subjects will be started at 5 µg/m²/day for the first 7 days of dosing followed by a dose step to 15 μg/m^2/day beginning at cycle 1.1 day 8 and continuing for the remainder of cycle 1.

An infusion interruption of more than 2 weeks due to an adverse event related to blinatumomab will lead to permanent discontinuation of treatment. In case of logistical difficulties, restart of treatment can be postponed for up to 7 additional days without resulting in permanent treatment discontinuation.

Any infusion interruption or dose modifications due to adverse event will be recorded in the eCRF.

Infusion interruption/dose modification guidelines for pediatric subjects in the expansion cohort will be the same as described above.

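### After a grade 2 or 3 neurologic event, children are barred from dose escalation by Protocol 6.5.2 but stepped back up by 2.3 and by the cycle 1.1 rule in 6.5.1.2

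*Protocol*

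**What the plan says.** Four pieces of protocol text bear on how a child restarts after a neurologic event.

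- **Section 6.5.2 (neurologic events).** For children it applies from grade 2 upward, when the event is related to blinatumomab. If the event has settled to grade 1 or lower within a week, "treatment may be restarted within 2 weeks, but not earlier than 3 days after infusion was stopped". Then "a new treatment cycle may be started after consultation with an Amgen medical monitor", at the lower dose of the child's cohort, and "There will be no dose escalations after blinatumomab treatment has restarted following an event".
- **Section 2.3 (pediatric risk assessment).** The paragraph on neurologic adverse events gives a dexamethasone regimen and ends: "Restart of blinatumomab treatment will be performed by an algorithm with step-wise dose increase until maintenance dose".
- **Section 6.5.1.2, general restart sentence.** The interruption triggers include "Grade 2 clinically relevant neurologic event related to blinatumomab, as defined in Appendix I", and a further bullet takes in any related, clinically relevant event of grade 3 or higher. After resolution to grade 1 or lower, blinatumomab "may be restarted at the lowest starting dose of the dose cohort for at least 7 days before increasing to a maximum of" 15 µg/m²/day.
- **Section 6.5.1.2, cycle 1.1 rule.** An adverse-event interruption of more than 7 days starts a new cycle, and a cycle with under 2 weeks of treatment must be repeated. The example given is that "if cycle 1 was interrupted on day 8 for more than 7 days, the next cycle will be denoted as cycle 1.1". Dosing in that cycle is 5 µg/m²/day "for the first 7 days of dosing followed by a dose step to" 15 µg/m²/day.

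Section 6.5.1.2 also requires permanent discontinuation for related grade 4 events that are not purely laboratory-defined. The restart question therefore concerns grades 2 and 3.

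**The concern.** Section 6.5.2 forbids escalation, 2.3 directs it, and the cycle 1.1 rule prescribes it on day 8. A site that follows either of the last two literally would raise the dose of a child whom the dedicated neurologic section keeps at the lower level. Section 2.3 itself counts neurologic events of grade 2 or 3 among the most medically significant adverse events seen with the drug.

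In this version of the protocol the point bears mainly on the expansion cohort. Its children receive 5-15 µg/m²/day (6.2.2.3.2), and 6.5.1.2 applies the same interruption rules to them.

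**Working it through.** There is no plan figure to reproduce. The check is a comparison of texts, followed by short dose arithmetic.

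**1. Is 6.5.2 against 2.3 a real conflict?** Both texts address neurologic events and both apply to children. One bars escalation after restart; the other says restart proceeds by step-wise increase to a maintenance dose. Neither mentions the other.

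**2. Does 6.5.1.2 exempt neurologic events?** It has one carve-out for Appendix I neurologic events. It closes the paragraph on dose reductions made at the investigator's judgment. The general restart sentence stands before that paragraph and the cycle 1.1 rule after it, so the carve-out reaches neither. The adult section (6.5.1.1) sends neurologic interruptions to 6.5.2; the pediatric section has no such pointer.

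**3. When do the cycle 1.1 rule and 6.5.2 both apply?**

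| Condition | Source |
|---|---|
| Less than 14 days of cycle 1 treatment | 6.5.1.2 |
| Interruption of more than 7 days | 6.5.1.2 |
| Restart no sooner than 3 and no later than 14 days after stopping | 6.5.2 |

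The overlap is a restart more than 7 and up to 14 days after stopping, following less than 14 days of cycle 1 treatment. It is narrow but not empty.

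**4. How strong is the general restart sentence?** It is permissive: restart is allowed, with 15 µg/m²/day as a ceiling. It does not require what 6.5.2 forbids, but it permits it.

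**5. Dose under each instruction, 5-15 µg/m²/day regimen.**

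- Continuing dose: 15 / 5 = 3.
- New 28-day infusion without escalation (6.5.2): 28 × 5 = 140 µg/m².
- New 28-day infusion under the cycle 1.1 rule: 7 × 5 + 21 × 15 = 35 + 315 = 350 µg/m².
- Ratio: 350 / 140 = 2.5; equivalently, 6.5.2 gives 40% of the cycle 1.1 amount.
- Any later full cycle: 28 × 5 = 140 against 28 × 15 = 420 µg/m², a ratio of 3.

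The 350 µg/m² figure belongs to the cycle 1.1 schedule. It does not carry over to interruptions under 7 days, for which 6.5.1.2 continues the same cycle.

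**The case against.** The best answer is that 6.5.2 was plainly meant to govern. It is the dedicated section, it names its pediatric threshold in its first sentence, and the neurologic row of Table 4 refers to it. Section 2.3 is background: it mentions an algorithm but gives no dose, schedule or grade, and it covers neurologic events more broadly than 6.5.2. The general restart sentence is permissive, so a site following 6.5.2 breaches nothing there. The cycle 1.1 overlap needs several conditions at once, and the adult cycle 1.1 text likewise has no neurologic exception at that point. A sponsor medical monitor must be consulted before a new cycle.

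Much of this stands. The intent is visible, the restart sentence is only a looser inconsistency, the cycle 1.1 conflict is narrow, and the consultation lowers the risk. It does not reconcile the texts:

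- The restart sentence in 2.3 is worded as an instruction, and the dexamethasone regimen just before it closely matches the pediatric neurologic row of Table 4. A reader has reason to take both as operational.
- The cycle 1.1 dosing is mandatory wording, with no neurologic exception and no pediatric pointer to 6.5.2. Adults at least have that pointer.
- The medical monitor would be consulting the same contradictory protocol.

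**Conclusion.** The concern holds. For children restarted after a related grade 2 or 3 neurologic event, 6.5.2 is contradicted directly by 2.3 and, in a narrow window, by the cycle 1.1 rule; the general restart sentence permits what 6.5.2 forbids. At stake is a threefold difference in continuing dose, and a 2.5-fold difference in cumulative dose where a new cycle follows the cycle 1.1 schedule.

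The threefold figure, as applied to 2.3, assumes that the maintenance dose there is the regimen's higher dose, which the section does not define. How often the situation would arise cannot be judged from the documents. Endpoints, sample size and analyses are unaffected. The text should be corrected because, followed as written, it could re-escalate a child whom the neurologic section holds at the lower dose.

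**What to change.** Keep 6.5.2 as it is and bring the other texts into line with it.

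- In 6.5.1.2, exempt Appendix I neurologic events from the sentence allowing restart and increase, and from the cycle 1.1 dose step.
- In 6.5.1.2, add a pointer to 6.5.2 for neurologic interruptions, as 6.5.1.1 has for adults.
- In 2.3, replace the step-wise increase in the neurologic paragraph with restart at the cohort's lower dose without later escalation, citing 6.5.2.

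The cost is protocol wording in two sections. Sample size and analysis do not change.

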## 6.6 Criteria for Discontinuation of Blinatumomab

Treatment with blinatumomab must be discontinued in the event of any of the following:

- Hematological or extramedullary relapse subsequent to achieving ≤ 5% bone marrow blasts on protocol treatment
  - Exception: subjects who develop isolated CNS leukemia relapse during treatment and who have not met the criteria for an event as defined above, may continue on study and receive additional CNS directed therapy in addition to their systemic protocol-specified therapy.
- Failure to achieve bone marrow response as defined by ≤ 5% blasts in the bone marrow within 2 treatment cycles
- Occurrence of an adverse event which makes discontinuation from treatment necessary due to protocol specified safety criteria or desirable in the investigator's and/or the subject's opinion
- Investigator's decision that a change of therapy (including immediate HSCT) is in the subjects best interest
- Administration of relevant non-permitted concomitant medications (Section 6.11)
- Investigator's decision that a subject does not benefit from treatment anymore (eg, non-response or development of progressive disease)
- Intercurrent medical condition, which in the opinion of the investigator or the subject precludes further treatment of the subject
- Withdrawal of subject's consent to study treatment

All reasons for treatment discontinuation will be documented in the eCRF. If a subject fails to keep the appointments for study visits, the investigator will document the reason and circumstances as completely and accurately as possible.

In case of premature treatment discontinuation, the assessments planned for day 29 (end of infusion) should be performed immediately. Exceptions: The CSF examination/prophylaxis does not have to be done in case of premature treatment discontinuation. Bone marrow aspiration/biopsy is not required in case of documented progressive disease. In addition, the safety follow-up visit should be performed 30 (± 3) days after the last dose of blinatumomab was administered or, if applicable, prior to the start of a new anti-leukemic treatment or alloHSCT, whichever occurs first. The subject will continue to be followed in long-term follow-up as described in Section 7.2.5.

Date: 20 March 2019 Page 56 of 122

## 6.7 Hepatotoxicity Stopping and Rechallenge Rules

Subjects with abnormal hepatic laboratory values (ie, ALP, AST, ALT, TBL), and/or international normalized ratio (INR), and/or signs/symptoms of hepatitis (as described below) may meet the criteria for withholding or permanent discontinuation of blinatumomab or other protocol-required therapies as specified in the guidance for industry Drug-Induced Liver Injury: Premarketing Clinical Evaluation, July 2009.

## 6.7.1 Criteria for Permanent Discontinuation of Blinatumomab and Other Protocol-required Therapies due to Potential Hepatotoxicity

Blinatumomab and other protocol-required therapies should be discontinued permanently and the subject should be followed according to the recommendations in Appendix A (Additional Safety Assessment Information) for possible drug induced liver injury (DILI), if ALL of the criteria below are met:

- TBL > 2x ULN or INR > 1.5
- AND increased AST or ALT from the relevant baseline value as specified below:

Baseline AST or ALT value	AST or ALT elevation
< ULN	> 3x ULN

- AND no other cause for the combination of the above laboratory abnormalities is immediately apparent; important alternative causes for elevated AST/ALT and/or TBL values include, but are not limited to:
  - Hepatobiliary tract disease
  - Viral hepatitis (eg, hepatitis A/B/C/D/E, Epstein-Barr virus, cytomegalovirus (CMV), herpes simplex virus, Varicella, toxoplasmosis, and parvovirus)
  - Right sided heart failure, hypotension or any cause of hypoxia to the liver causing ischemia
  - Exposure to hepatotoxic agents/drugs or hepatotoxins, including herbal and dietary supplements, plants and mushrooms
  - Heritable disorders causing impaired glucuronidation (eg, Gilbert's syndrome, Crigler-Najjar syndrome) and drugs that inhibit bilirubin glucuronidation (eg, indinavir, atazanavir)
  - Alpha-one antitrypsin deficiency
  - Alcoholic hepatitis
  - Autoimmune hepatitis
  - Wilson's disease and hemochromatosis
  - Nonalcoholic fatty liver disease including steatohepatitis (NASH)
  - Nonhepatic causes (eg, rhabdomylosis, hemolysis)
  - Cytokine release syndrome

Date: 20 March 2019 Page 57 of 122

If an alternative cause for hepatotoxicity is identified or less stringent conditions developed than what are noted above, determine (based on patient population and/or severity of the hepatotoxicity or event) if blinatumomab and other protocol-required therapies should be withheld or permanently discontinued, as deemed appropriate for the safety of the subject.

# 6.7.2 Criteria for Conditional Withholding of Blinatumomab and Other Protocol-required Therapies due to Potential Hepatotoxicity

For subjects who do not meet the criteria for permanent discontinuation of blinatumomab outlined above and have no underlying liver disease, and eligibility criteria concerning transaminases and TBL at baseline or subjects with underlying liver disease and baseline abnormal transaminases, the following rules are recommended for withholding of blinatumomab and other protocol-required therapies:

Elevation of either AST or ALT according to the following schedule:

Baseline AST or ALT value	AST or ALT elevation
Any	> 8x ULN at any time
Any	> 5x ULN but < 8x ULN for ≥ 2 weeks
Any	> 5x ULN but < 8x ULN and unable to adhere to enhanced monitoring schedule
Any	> 3x ULN with clinical signs or symptoms that are consistent with hepatitis (such as right upper quadrant pain/tenderness, fever, nausea, vomiting, jaundice).

OR: TBL > 3x ULN at any time
 OR: ALP > 8x ULN at any time

Blinatumomab and other protocol-required therapies, as appropriate should be withheld pending investigation into alternative causes of DILI. If investigational product(s) is withheld, the subject is to be followed according to recommendations in Appendix A for possible DILI. Rechallenge may be considered if an alternative cause for impaired liver tests (ALT, AST, ALP) and/or elevated TBL, is discovered and the laboratory abnormalities resolve to normal or baseline (Section 6.7.3).

## 6.7.3 Criteria for Rechallenge of Blinatumomab and Other Protocol-required Therapies After Potential Hepatotoxicity

The decision to rechallenge the subject should be discussed and agreed upon unanimously by the subject, investigator, and Amgen.

Product: Blinatumomab

Date: 20 March 2019 Page 58 of 122

If signs or symptoms recur with rechallenge, then blinatumomab and other protocol-required therapies, as appropriate, should be permanently discontinued. Subjects who clearly meet the criteria for permanent discontinuation (as described in Section 8) should never be rechallenged.

### 6.8 **Concomitant Therapy**

Throughout the study, investigators may prescribe any concomitant medications or treatments deemed necessary to provide adequate supportive care except for those listed in Section 6.11.

Relevant concomitant therapies (eg, steroids/pre-phase therapy, immunoglobulins, G-CSF, antibiotics, antivirals, antifungals, CSF prophylaxis medication, anticonvulsants) are to be collected from signing of the ICF through the safety follow-up period. Following the safety follow-up visit, only medications taken for the treatment of ALL will be collected.

### 6.8.1 **Hydration During the Treatment Period**

Because of the high tumor load, subjects should receive adequate hydration according to institutional guidelines.

### 6.8.2 **Fever Management**

Nonsteroidal anti-inflammatory drugs (NSAIDs) should be avoided if possible because they are a potential cause of endothelial stress and could potentially affect T-cells that are required for blinatumomab action. For symptomatic relief of fevers due to any cause (eg, infection, drug fever) the recommended first choices for fever management are paracetamol/acetaminophen and/or dexamethasone. The dexamethasone dose should be reduced step-wise as soon as the fever is resolved. If these are not sufficiently effective, pethidin/meperidine is recommended. For pethidin/meperidine, adequate antiemetic prophylaxis should be administered. The treating physician should also use their clinical judgment to determine the underlying cause of the fever and treatment. For instance, in the case of fever due to infection one should consider the use of antibiotics and avoid the use of dexamethasone.

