### 6.5.1 Infusion Interruption/Dose Modification due to Adverse Events

### 6.5.1.1 **Adult Subjects**

Blinatumomab treatment will be interrupted until the following non-DLT events resolve to ≤ grade 1:

- Grade 3 or higher CRS, tumor lysis syndrome, and disseminated intravascular coagulation (DIC)/coagulopathy related to blinatumomab
- Grade 3 or higher clinically relevant neurologic event related to blinatumomab, as defined in Appendix I

In the event of a grade 3 or higher infection, blinatumomab will be interrupted until the infection is adequately controlled or resolved per the opinion of the investigator.

For interruptions or dose modifications due to neurologic events (as defined in Appendix I), see Section 6.5.2.

CTCAE grade 4 adverse events not defined solely based on laboratory parameters at least possibly related to blinatumomab will require permanent discontinuation of blinatumomab. Independent investigator assessment should be used to determine the risk:benefit for each individual subject to continue blinatumomab therapy with or without dose reduction or discontinue therapy for:

- Grade 4 adverse events that are numerically defined laboratory parameters
- All other grade 3 adverse events and clinically significant laboratory value changes

If the adverse event resolves to ≤ grade 1 within 1 week, blinatumomab may be restarted at the lower assigned dose level for the subject's assigned cohort for at least 7 days before increasing to the higher assigned dose level.

Restart of the infusion should be performed under supervision of the investigator. Before blinatumomab is restarted, premedication with dexamethasone must be administered as described in Table 4. The subject should be observed overnight for possible side effects after the restart.

In addition to the events described above, the dose may be temporarily or permanently reduced to the lower assigned dose level for the subject's assigned cohort if, by the investigator's judgment, it is necessary for safety reasons. After at least 7 days of dosing at the lower assigned dose level, the dose may be increased to the higher assigned dose level, or treatment may be continued at the lower assigned dose level

Product: Blinatumomab Date: 20 March 2019

after consultation with an Amgen medical monitor. The subject will continue to be treated at the adjusted blinatumomab dose and evaluated in the originally assigned cohort.

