## 6.11 Excluded Treatments and/or Procedures During Study Period

The following medications are not permitted during a subject's participation during treatment phase (including the induction and consolidation phases of treatment) of this study:

- Tyrosine kinase inhibitor therapy (eg, imatinib, dasatinib, niolotinib, bosutinib, and ponatinib) are not permitted during treatment with blinatumomab
- Any anti-tumor therapy other than the blinatumomab:
  - Cytotoxic and/or cytostatic drugs
  - Radiation therapy
  - Immunotherapy
- Chronic systemic (> 7 days) high-dose corticosteroid therapy (dexamethasone > 24 mg/day or equivalent)
- Any other immunosuppressive therapies (except for transient use of corticosteroids)
- Any other investigational agent

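### Protocol 6.8.2 contradicts itself on dexamethasone for infectious fever: one sentence recommends it as a possible first choice, another says to avoid it

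*Protocol*

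**What the plan says.** Fever management is one paragraph, Protocol section 6.8.2. After advising against NSAIDs where possible, it gives a general recommendation: "For symptomatic relief of fevers due to any cause (eg, infection, drug fever) the recommended first choices for fever management are paracetamol/acetaminophen and/or dexamethasone". The taper sentence follows: "The dexamethasone dose should be reduced step-wise as soon as the fever is resolved". Pethidine/meperidine is then recommended if the first choices do not work well enough. The paragraph next turns to judgment: "The treating physician should also use their clinical judgment to determine the underlying cause of the fever and treatment". It closes with an illustration of that judgment: "in the case of fever due to infection one should consider the use of antibiotics and avoid the use of dexamethasone".

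The protocol regards infection during treatment as foreseeable. Section 2.3 says that an increased risk may exist, citing long-term intravenous access and adding that "blinatumomab-mediated depletion of B cells could result in an increased infection rate". Appendix H lists bacterial, fungal and viral infections, pneumonia and sepsis among the known adverse reactions.

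**The concern.** A subject with infectious fever falls under both sentences. By the general sentence, dexamethasone is among the recommended first choices. By the closing sentence, it should be avoided. An investigator who looks up the paragraph to decide on a steroid for such a subject finds support for either course.

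What is at stake is the clarity of a safety instruction, in a setting where the protocol itself anticipates fever and infection. Sites could act differently in good faith, and a monitor would have no clear standard for calling either action a departure from the protocol.

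**Working it through.** There is no figure in the plan to reproduce and no formula applies. The check compares the sentences and then looks for any other text that settles the matter.

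**Scope.** The general sentence covers fever of any cause and gives two examples, infection first and drug fever second. The closing sentence covers fever caused by infection. The second group lies wholly inside the first, and the general sentence says so by naming it.

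**What each possible action does under the two sentences, for a subject with infectious fever:**

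| Antipyretic given | General sentence | Closing sentence |
|---|---|---|
| Paracetamol/acetaminophen alone | consistent | consistent |
| Dexamethasone alone | consistent | departs |
| Both together | consistent | departs |

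The general sentence permits one agent or both, so three choices are consistent with it. Two of the three depart from the closing sentence. The contradiction is therefore real, but it is confined to sites that use dexamethasone.

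**Does the rest of the paragraph resolve it?** The taper sentence carries no condition about infection, and neither does the step to pethidine/meperidine. The judgment sentence asks the physician to establish the cause. Once infection is established, both recommendations still apply to it.

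**Does any other section resolve it?**
- Table 4 has rows for pre-phase, pre-dose, restart after interruption, cytokine release and neurologic events. It has none for fever.
- Section 6.5.1.1 concerns study drug only: "In the event of a grade 3 or higher infection, blinatumomab will be interrupted until the infection is adequately controlled or resolved". It is silent on steroids for fever.
- Section 6.8 allows any supportive medication that section 6.11 does not list.
- Section 6.11 bars high-dose corticosteroids (dexamethasone above 24 mg/day or equivalent) only when given for more than 7 days. It allows transient corticosteroid use and does not mention infection.
- The SAP summarises concomitant medications by preferred term (section 10.7.6) and gives no rule on fever treatment.

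None of these says which sentence of 6.8.2 governs.

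**Size.** An estimate would need the proportion of subjects whose fever is caused by infection. Neither document gives one.

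**The case against.** The best defence is that the paragraph moves from symptomatic relief to treatment directed at the cause. The closing sentence is offered as an example of clinical judgment, is the more specific of the two, and comes last, so a reader would naturally let it prevail once infection is identified. Both sentences are recommendations, not mandates. The choice of agents also lets any site comply with both by leaving dexamethasone out.

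Much of this stands. It rules out a stronger reading that a reader might infer, that subjects with infection face two orders which cannot both be obeyed. They do not.

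What the defence does not explain is why infection appears as an example in the general sentence. Had that sentence been silent on infection, the closing sentence would be an ordinary exception. As worded, it withdraws something the general sentence expressly recommends, with no wording to mark it as an exception. Nor is the advice to avoid dexamethasone limited to cause-directed treatment, so separating that from symptomatic relief does not remove the clash.

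**Conclusion.** Section 6.8.2 is inconsistent on dexamethasone for infectious fever, and the two sentences must be reconciled. This is a clarification of a safety instruction. It alters no endpoint definition, sample size, error rate or analysis. The conclusion rests only on the wording of the paragraph and on the absence of a governing rule elsewhere in the two documents.

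Three larger consequences might be inferred, and the documents do not support them:

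- **An effect on the dose-limiting toxicity assessment.** Section 6.2.2.1 excludes fever and infection of grade 3 or higher from DLTs. It also generally excludes grade 3 or higher events in Appendices H and I, which include cytokine release and neurologic terms, unless the Data Review Committee finds them substantially different from the known profile.
- **Meaningful extra anti-leukemic exposure before the response marrow.** Dexamethasone is already given by protocol: up to 5 days of pre-phase treatment with a ceiling of 24 mg/day, and 20 mg IV before each adult cycle and dose step. Nothing quantifies what fever treatment would add. Steroid use is recorded through safety follow-up (section 6.8).
- **A count of affected expansion subjects.** Section 2.1.2 reports pyrexia in 74% and grade 3 or higher febrile neutropenia in 15% of 39 children. Multiplying by about 65 gives 65 × 0.74 = 48.1 and 65 × 0.15 = 9.75. These are not counts of infectious fever. The pyrexia figure is regardless of cause, in a passage that describes the events as mostly flu-like and consistent with the drug's mechanism. Febrile neutropenia is not documented infection. The rates come from children in another study, whereas the expansion cohort mixes adults and children and its size is not restricted.

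**What to change.** Amend section 6.8.2 so that a single instruction on dexamethasone applies to fever caused by infection. Either the examples in the general sentence are brought into line with the closing sentence, or the closing sentence is brought into line with the general one. If the sponsor intends a general rule with an exception, the text should say so in explicit terms. Which instruction is right is for the sponsor's clinicians, and none is proposed here.

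The cost is one or two sentences in one paragraph. No change to the SAP, the schedule of assessments or data collection follows from it.
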